2.1 Background

Stroke survivors are not routinely offered structured, intensive, and multidisciplinary rehabilitative programs in the community (1-3). Rarely are they also offered support to improve self-management skills alongside intensive rehabilitative training (2,4-5). This may be due to the lack of knowledge about the amount of therapy they should participate in (6-8). Or in part due to the 'clear and impressive void' in current literature on the development of programs for community dwelling stroke survivors to improve their physical function, mobility, and quality of life beyond acute and subacute rehabilitative settings (1). The Australian Stroke Guidelines have not yet indicated the recommended amount of practice in community-based rehabilitation, perpetuating the difficulty for community rehabilitation to deliver appropriate care in the chronic stages of recovery (1,9). The lack of research into ideal practice in the chronic phase may also result from a previously held belief that functional recovery after stroke

plateaus after 12 months, despite the evidence suggesting that improvement is possible later than this (1). In the community, increasing amounts of practice is typically through the provision of group programs as they are feasible to implement, cost efficient and can be replicated multiple times per week (1,10-12). Circuit and group classes do improve physical activity, however, do not routinely result in ongoing changes in mobility, independence, or quality of life in community dwelling stroke survivors in long term follow up (10-12).

At the study site, an intensive program is already offered, however there are numerous limitations including noting that it is an option rarely selected by clients, not structured, and simply includes more frequent appointments. The current program offering has recently been revised to include more structured support and include multidisciplinary and self-management interventions. It is important that new programs be evaluated to determine acceptability in this population and whether this type of training results in positive mobility outcomes. New programs which offer this level of training warrant further investigation and ultimately must offer stroke survivors in the community an option of training which is aspirational towards goals and pragmatic in application (13).

2.2 Rationale for Study

There was recent success of a single group study which was able to deliver an 'intensive' bout of therapy, offering 90 hours of upper limb therapy over three weeks using a multidisciplinary team (13). They observed improvement in upper limb function in a proportion of stroke survivors, these improvements were sustained at the six months follow up and were hypothesized to also be the result of building self-efficacy and education into the program (4, 13). This study suggests the feasibility of intensive and multidisciplinary models of therapy which improve upper limb activities may be suitable for community dwelling stroke survivors. Rehabilitation centres in the community, may be uniquely primed to offer the intensity of practice and the support to improve mobility for stroke survivors in the long term (1,13). Thus, there is a need for further investigation into intensive programs offered by these settings to determine what is an accepted model of training and what parameters are required to improve mobility.

The complex nature of stroke means that survivors experience multifaceted barriers to physical activity and adequate rehabilitation post stroke, including lack of motivation, external support, and stroke related impairments (14). New models of therapy in the community must address these barriers to physical activity in more wholistic methods, possibly using the breadth of the multidisciplinary team to better deliver long term care (14, 15). Currently the Australian Clinical Guidelines for Stroke makes no recommendation on the explicit need for ongoing multidisciplinary intervention throughout the rehabilitation process, including community-based rehabilitation (9,15). This is possibly due to the limited number and low quality of previous studies evaluating their efficacy and utility beyond primary care (16). Thus, the justification for an ongoing multidisciplinary intervention may be drawn from application of the International Classification of Functioning, Disability and Health (ICF) model (17). Chronic conditions and disabilities such as stroke have several characteristics which impact all domains of the ICF (17). There is an apparent need for community interventions which better address the diverse barriers to prolonged inactivity experienced by stroke survivors and resist the tendency to silo disciplines into addressing only certain aspects of the ICF domain (14,17).

Self-management is the process by which an individual is enabled to manage all the aspects of their health condition through building new health behaviours and supporting skills. Research into the utility

of self-management programs to enable ongoing self-management in stroke populations lags other chronic conditions such COPD or arthritis (19,20). Only half the number of stroke survivors in Australia were provided information about self-management programs when discharged from formal rehabilitation (21). This is despite most health professionals acknowledging that the level of structured support post discharge significantly declines (20-21). The Taking Charge After Stroke (TACAs) trial showed that self-efficacy and independence after stroke matters to stroke survivors in the community (19). A study by Marsden and colleagues (2010) showed integrating self-management and task specific training delivered by a multidisciplinary team for rural community dwelling stroke survivors improves physical performance and quality of life (2).

It is hypothesised that with the support of a self-management program delivered with the benefits of access to a multidisciplinary team and intensive training, stroke survivors living in the community may build the self-efficacy and skills required to better manage their condition. It is hoped this novel method offers an alternative to improve mobility and function and provide better tailored goal directed training.

2.3 Research aims

The primary aim of this study is to determine the feasibility of a short duration, intensive multidisciplinary therapy mobility program, delivered using a self-management approach for stroke survivors living in the community.

2.4 Research questions

- 1.Is it feasible to deliver a multidisciplinary, short duration, intensive program for people after stroke using a self-management approach (in terms of adherence, acceptability, cost, and safety) in a community setting?
- 2. Does this approach warrant further investigation, indicated by an improvement of more than 10% in the main secondary measure of the study, mobility pre and post intervention?

2.5 Hypothesis

We hypothesise that it will be feasible to implement a multidisciplinary, intensive, short duration therapy program and that this program will have a high adherence rate and acceptability. It is likely to offer an alternative option to regular therapy programs currently provided in community rehabilitation (typically either non-existent or longer duration, less frequent and not intense). In addition, community-dwelling stroke survivors may prefer this mode of therapy delivery because it offers a different structure of multidisciplinary and self-management support alongside intensity of practice. We anticipate that there will be no significant safety issues or adverse events associated with this type of program.

3 Study Design

3.1 Type of Study

A prospective single group pre and post intervention study will be conducted with participants recruited from Concentric Rehabilitation Centre at two Sydney sites (Burwood and Bella Vista) who have decided to participate in an intensive program run by the rehabilitation centre.

3.2 Study Design

The study will look at the feasibility of providing this type of training offered to clients attending the program at the study sites. As part of the intensive program, participants will undertake 45 hours (three hours for five consecutive days over three weeks) of intensive, multidisciplinary practice both in the clinic and at home. At-home therapy will be delivered by video-guided exercise programs or individualised exercise programs. The primary outcome measure for this study will be feasibility, measured by adherence, acceptability, cost and safety. The secondary outcome measures for this study will be mobility, quality of life, self-efficacy skills and goal attainment. Outcome measures will be collected just prior commencement (week 0) (T1), midpoint (second week) (T2), upon completion of the intensive program (third week) (T3) and three weeks post intensive program (T4).

3.2.1 Risks and Benefits associated with the study

Participation in this research study is considered low risk. It may be inconvenient for participants, due to the extra time required to fill out consent forms and surveys. This time will be allocated outside therapy and program time.

The potential benefits associated with this study include gains in knowledge about the feasibility of this type of training for community populations who have survived stroke. This includes a better understanding of the amount of acceptable training and potential clinical benefits in mobility, building self-efficacy and quality of life into therapy approaches and as drivers of outcomes. This study has the potential to inform future studies, programs and research.

3.3 Study Duration

The study will run for approximately 12 months including study design, recruitment, enrolment, screening, consent, intervention, follow up period, data collection and analysis. The total data collection period is 7 weeks from (T1) to (T4) including the initial assessment (T1) through to follow up three weeks after intervention with participants at (T4).

3.4 Flow of Study

An allied health clinician from the study site will collect demographic information such as age, gender, side of hemiparesis and time post stroke by asking the participant in an initial assessment and using the study demographic form (T1). In the same assessment (T1), the abilities of the participant using the Motor Assessment Scale for Stroke (MAS), Short Physical Performance Battery (SPPB), 2 Minute Walk Test (2MWT), Exercise Self Efficacy Scale (ESES) and the 12-Item Short Form Survey (SF-12) will be taken and recorded in the participant rehabilitation centre files (22-26). The clinician with the participant will then identify an 'area of difficulty' based on an individual activity limitation or participation. The clinician with the participant will establish one primary physical goal for the intervention and up to two secondary goals and score them based on the Goal Attainment Scale (GAS) (27). These outcomes and goals will be recorded the participant's rehabilitation centre files, handed over to treating therapists for the program and recorded in the participant's paper workbook.

Participants will then undergo the intervention and clinicians will record in their practice sheets the exercises completed and participant's perceived rating of exertion for each exercise for the duration

of the intensive program (via the Borg Rating of Perceived Exertion (RPE scale)) (28). After two weeks of the intensive program (T2), a summary of performance outcomes (SPPB and 2MWT) will be taken as an indicator of progress by an allied health clinician (23,24). These two outcome measures will be recorded in the participant's rehabilitation centre files and in a participant's paper workbook.

After the three-week intervention period (T3), an allied health clinician blinded to the preintervention outcome measures of the program will reassess the initial assessment measures (MAS,
SPPB, 2MWT and SF-12, ESES) and rescore the goals (using the GAS) (22-27). These outcomes, along
with the Borg perceived exertion ratings will be recorded in the participant's rehabilitation centre
files (28). Participants will also be given a post intervention survey by the allied health clinician to
determine the intervention's feasibility and effect on self-management and quality of life (this
survey is detailed below). This survey will be completed in allocated time outside the intervention
either at home or in the clinic and if needed an allied health clinician or carer will be available to
support filling out the survey and collecting the surveys from participant. Completed surveys will be
filed in the participant's rehabilitation centre file and in a participant's paper workbook. Participants
will be followed up in three weeks (T4) by the same allied health clinician, who will complete a
follow up assessment to obtain follow up outcome measures (MAS, SPPB, 2MWT, ESES SF-12) and
participants will be asked to complete the same survey again under the same conditions and
provisional support as the first survey (22-26). The results from the survey and the outcome
measures will be filed in the participant's rehabilitation centre file.

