3.5.1 Primary Outcome Measures

Feasibility of delivering the intervention will be in assessed using measures of adherence, acceptability, cost and safety. This will be collected by an allied health clinician at timepoints (T2), (T3) and (T4).

Adherence

Adherence will be measured by each participant in a workbook. The two measures of adherence will be percentage of sessions attended and number of repetitions completed per session will recorded in the participant's rehabilitation centre files. Attaining a personal best is encouraged in each session.

Acceptability

Acceptability will be determined via two methods, extracting perceived exertion (via the Borg Rating of Perceived Exertion (RPE scale)) from the practice sheets of participants at the study site at timepoints (T2), (T3) and (T4) and via purpose-built paper survey post intervention at timepoints (T3) and (T4) (28). The practice sheets will be stored on the participant's rehabilitation centre files. The paper survey will be provided in person by an allied health clinician from the study site. A paper survey was selected as in previous research at the study site there was a poor response to an electronic survey with participants requesting a paper-based survey. We expect the survey to take approximately 10 minutes to complete, participants will be given support to complete the study in clinic or may take the survey home to complete in time allocated outside the intervention. The

participant may receive support from a family member or carer. If requested, the allied health clinician may allocate time to assist in completion of the survey. Using a Likert scale, the survey will ask four questions:

- i) Were you satisfied with the program?
- ii) How easy was it to participate in the program?
- iii) Did the program give you adequate support?
- iv) Would you recommend the program?

They will also be given free text to input an answer to the following questions:

- i) What did you like or dislike about the multidisciplinary aspect of the program?
- ii) What did you like or dislike about the inclusion of Take Charge and participant workbook in the program?
- iii) What did you like or dislike about the amount of practice that was required?

Cost

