Cost will be reported by calculating the cost of the program per individual participant based on standard clinic fees. Participants will be charged for the therapeutic program as per usual care at the study site. Participants will not be charged for any research activities include assessments, surveys or research related follow up.

Safety

Safety will be monitored during training sessions by a member of the rehabilitation team and participants will be asked to log any events occurring at home in their participant workbook. All incidents will be recorded in the rehabilitation centre files and reported by the research team.

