6.2 Data Analysis

De-identified data analysis will be conducted using SPSS Version 25. Demographic data will be

reported via descriptive statistics. Adherence data will be calculated from each week and from week 0 (T1) to week 3 (T2) and will be reported as mean repetitions per hour, session, and week and then as a percentage of overall sessions attended. Acceptability and self-management data will be taken from the surveys and will be reported as frequencies comparing time points week 3 (T3) and week 6 (T4). Acceptability data from the practice sheets use will be calculated from each week and from week 0 (T1) to week 3 (T3) and will be reported as mean values per week and then as a percentage overall. Paired t-tests will be used to analyse within group change over time for the clinical outcomes between week 0 (T1) to week 3 (T3) and between week 0 (T1) to week 6 (T4). Differences will be reported as a mean and 95% confidence interval.

7 Research Outcomes and Future Plans

Participants will have the opportunity to review their initial (T1) and post intervention (T3, T4) results with their treating allied health clinician (as per usual care at the study site). A publication and conference presentation are expected from this project to satisfy the requirement of the Master by Research candidature. Participants who have consented to participation in the research will be informed that only de-identified group data will be presented.

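### The completed T3 acceptability survey is filed in the participant's own workbook, so T3 answers may be at hand when the same survey is repeated at T4, and the T3-T4 comparison could lean towards no change

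*Protocol*

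**What the plan says.** The acceptability survey has four Likert items and three free-text questions and is given at T3 and T4 (Protocol 3.5.1). Under 3.4 it is completed "either at home or in the clinic and if needed an allied health clinician or carer will be available to" help with it, and 3.5.1 confirms that participants "may take the survey home to complete in time allocated outside the intervention".

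After completion at T3 the survey is "filed in the participant's rehabilitation centre file and in a participant's paper workbook". At the three-week follow-up, "participants will be asked to complete the same survey again under the same conditions and" with the same help on offer. For T4, 3.4 names one place of filing only: the survey results and outcome "measures will be filed in the participant's rehabilitation centre file".

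The workbook is a document that participants use. Section 3.5.1 has them record adherence in it, and for safety "participants will be asked to log any events occurring at home in their participant workbook".

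Section 6.2 then states that the survey data "will be reported as frequencies comparing time points week 3 (T3) and week 6 (T4". No test or decision rule is attached to that comparison.

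**The concern.** In this survey the participant is the rater. Section 3.4 puts the rater's first set of answers into a document that the rater uses, and then asks for a second set on the same form three weeks later. If the first set is in view, some answers at T4 may be copied or adjusted for consistency.

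What is at stake is the meaning of the second survey. Acceptability is one of the four components of the primary outcome, feasibility. Repeating the survey is worthwhile only if it can show whether views hold once the program is over. Stable frequencies would be hard to interpret if they could reflect either stable views or a form that was consulted.

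**Working it through.** The protocol gives no figure for this comparison, so there is nothing to reproduce. The check is a reading of the sections together, followed by an illustration of size.

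**Step 1: are the earlier answers in the workbook?** Yes. Section 3.4 says so expressly for T3.

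**Step 2: is the T4 form the same, and can it be completed away from supervision?** Yes to both. Section 3.4 repeats the same survey under the same conditions, and those conditions include completion at home.

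**Step 3: who holds the workbook between T3 and T4?** The protocol does not say.

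- Pointing towards the participant: home events are logged in the workbook, and 3.5.1 has the feasibility measures, safety among them, collected at T4 as well as at T2 and T3. A home log that serves T4 would have to stay with the participant.
- Pointing the other way: 3.4 has a clinician or carer available to collect the surveys, and 6.1 has paper data collected after the intervention. However, 6.1 does not name the workbook or place that collection before T4.

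**Step 4: does the workbook copy serve the analysis?** No use of it is stated. Section 3.5 extracts outcome measures from the centre file, which already holds the T3 survey.

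**Step 5: direction and size.** Inputs:

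- n = 15, the approximate sample size in 5.5
- 12 satisfied at T3 (assumed)
- 8 truly satisfied at T4, all 4 changes being in the same direction (assumed)
- c = share of those 4 who repeat their T3 answer (assumed, shown over its full range)

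Reported number satisfied at T4 = 12 - (1 - c) × 4. Reported fall = (1 - c) × 4.

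| c | Reported satisfied at T4 | Reported fall (true fall 4) |
|---|---|---|
| 0 | 12 - 4 = 8 of 15 (53%) | 4 |
| 0.25 | 12 - 3 = 9 of 15 (60%) | 3 |
| 0.5 | 12 - 2 = 10 of 15 (67%) | 2 |
| 1 | 12 - 0 = 12 of 15 (80%) | 0 |

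More generally, if a share c of participants repeat their T3 answers whether or not their views changed, the expected observed change is (1 - c) times the true change. Any c above 0 pulls towards no change, for a rise as well as for a fall. If the workbook is not available at T4, this route gives c = 0.

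**The case against.** The strongest objection is that the deciding link is missing. Nothing in the protocol states that the participant has the workbook, with the T3 survey in it, when answering at T4. Its documented uses may end with the three-week program, and the fact that only the centre file is named at T4 fits a workbook no longer in use. This stands, and it makes the bias conditional.

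It is also fair that little is exposed. Research question 1 asks whether the program is acceptable, not whether acceptability changes. The T3 answers come before any filing, and the other acceptability measure, perceived exertion, is taken from practice sheets. What remains is a descriptive comparison in about 15 people. Ordinary recall over three weeks could produce some of the same similarity, and a filing rule would not remove that.

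A reader might also infer that the self-reported exercise self-efficacy and SF-12 results are compromised in the same way, because the T1 outcomes and goals are "handed over to treating therapists for the program and recorded in the participant's paper workbook". The protocol does not support that. It says that outcomes are recorded, not item responses, and a total score does not allow item answers to be copied. The T3 scores go to the centre file only. No direction of bias follows, and the documents give nothing from which to size an effect on the paired intervals.

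None of this removes the narrower point. Section 3.4 contains an explicit instruction that places earlier answers where the rater may see them before a planned repeat, and no purpose is stated for it. This is something the protocol fixes badly, not a detail left to an analysis plan.

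**Conclusion.** The point holds in a limited form. The filing instruction in 3.4 creates an avoidable risk that T3 answers are at hand at T4, in which case the comparison in 6.2 could be biased towards no change. It would go too far to say that the comparison is biased, or that the feasibility conclusion is undermined. The first depends on who holds the workbook, which the protocol leaves open. The second fails because T3 acceptability and the exertion ratings are untouched.

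The size cannot be derived from the protocol. Under the assumed true fall of 4 in 15, the reported fall lies anywhere from 4 (no answers repeated) to 0 (all repeated). In a sample this small, two repeated forms are enough to halve it. This is a minor matter, worth correcting because correction is almost free.

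**What to change.** In 3.4, state that the completed T3 survey is filed in the rehabilitation centre file only, as is already done at T4. Alternatively, state that it is removed from the workbook before T4.

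Nothing else needs to change. The T1 and T2 outcomes and the goals can stay in the workbook, where they serve the self-management approach, and the review of results with the treating clinician in section 7 can stand as written.

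The cost is one sentence. No data are lost, because outcomes are extracted from the centre file, and no extra staff time or visits are needed. If any participants have already passed T3 under the present wording, the report should say so and note that their T3 answers may have been available to them at T4.
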